4.3.2. Main Analytical Approach

The primary endpoint is the difference in the average number of MBDs per week during the Study Period 2 (Weeks 15 to 18), compared to the Study Period 1 (Weeks 5 and 6). The average of the Week 5 average number of MBDs and Week 6 average number of MBDs will be considered baseline. The change for each of average number of MBDs of each Week 15, Week 16, Week 17, and Week 18 will then be calculated from the averaged baseline. MBD is defined as no insulin dose from 1 hour prior to through 1 hour after the start of a glucose excursion, where a glucose excursion is defined as a >70 mg/dL (>3.9 mmol/L) rise within 2 hours, not preceded by a value <70 mg/dL (<3.9 mmol/L).

The average MBDs per week will be calculated for:

- Weeks 5 and 6 for Study Period 1 (masked), and
- Weeks 15 to 18 for Study Period 2 (unmasked).

The actual MBDs and change from baseline will be summarized descriptively by study period and by week, and presented in a table.

The analyses for the primary endpoint will be conducted using a mixed-effect models for repeated measures (MMRM) using average MBD of each week (Weeks 5–6 and Weeks 15–18). The study period will be a fixed effect, baseline body mass index (BMI) and baseline HbA1c as covariates, and subject as the random effect. The repeated measure will be time, as measured in weeks (2 weeks in Study Period 1 and 4 weeks in Study Period 2 for each participant). The primary analysis will occur in the main analysis set and repeated in the sensitivity analysis set.

The MMRM model will be programmed using proc mixed in SAS Software version 9.4. The details of the model, specifically the chosen covariance structure, is subject to change based on findings during model building in SAS Software version 9.4. An unstructured covariance structure will be used to model the within-participant errors. If this structure fails to converge, the following covariance structures will be used in order until one converges:

- Toeplitz with heterogeneity
- autoregressive with heterogeneity
- compound symmetry with heterogeneous variances
- Toeplitz
- autoregressive, and
- compound symmetry without heterogeneous variances.

An example data structure excerpt regarding the primary efficacy endpoint for a hypothetical Subject 1 will be similar to Table 4.1.

Table 4.1. Data Structure Example

Usubjid	Week	StudyPeriod	BaseBMI	BaseHbA1c	Weekly Average MBD	Baseline MBD	Change in MBD
1	Week 5	Study Period	28.5	7.2	10.3	(10.3+9.6)/2=9.95	
1	Week 6	Study Period	28.5	7.2	9.6		
1	Week 15	Study Period 2	28.5	7.2	10.1	9.95	0.15
1	Week 16	Study Period 2	28.5	7.2	8.2	9.95	1.75

Usubjid	Week	StudyPeriod	BaseBMI	BaseHbA1c	Weekly Average MBD	Baseline MBD	Change in MBD
1	Week 17	Study Period	28.5	7.2	7.6	9.95	2.35
1	Week 18	Study Period 2	28.5	7.2	5.2	9.95	4.75

Abbreviations: BaseBMI = baseline body mass index; BaseHbA1c = baseline glycated hemoglobin; MBD = missed bolus dose; Usubjid = unique subject identification.

Based on the data structure above, example SAS Software version 9.4 program code for the MMRM is as follows:

```
proc mixed data = <data>;
    Class StudyPeriod week usubjid;
    Model Weekly_Average_MBD = StudyPeriod BaseBMI BaseHbA1c week/
    ddfm = kenwordroger;
    Random usubjid / subject = usubjid;
    Repeated Week/ subject = usubjid type = un rcorr;
    Lsmeans StudyPeriod/diff cl pdiff;
run;
```

In this MMRM, the model statement contains the outcome, the fixed effect (study period), and the covariates (baseline BMI and baseline HbA1c). The option ddfm specifies the method for computing the denominator degrees of freedom. The repeated statement handles the effect of time (there will be 1 measurement in Study Period 1 and 4 measurements in Study Period 2 for each participant) and options specify both the subject ID variable as well as the type of covariance structure that will be used. The LSMeans statement will output the model-adjusted least square means for each study period (masked and unmasked). The difference estimate of the least square means between Study Period 2 and Study Period 1, along with 2-sided 95% Confidence Interval (CI) and the p-value will also be estimated and reported.

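### The primary repeated-measures model pairs a participant random intercept with an unstructured covariance, which leaves one redundant parameter, and one SAP sentence loosens the fixed order of covariance structures

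*SAP*

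**What the plan says.** SAP 4.3.2 describes the primary model in text and in example code, and the two agree on the covariance.

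- **Random part.** The text has "subject as the random effect"; the code has "Random usubjid / subject = usubjid". With participant as both effect and subject, this is a random participant intercept.
- **Residual part.** The text says "An unstructured covariance structure will be used to model the within-participant errors"; the code has "Repeated Week/ subject = usubjid type = un rcorr".
- **Number of weekly values.** The text gives "2 weeks in Study Period 1 and 4 weeks in Study Period 2 for each participant", and Table 4.1 is laid out with Weeks 5, 6 and 15 to 18. The paragraph after the code says instead that "there will be 1 measurement in Study Period 1 and 4 measurements in Study Period 2 for each participant".
- **Fallback rule.** "If this structure fails to converge, the following covariance structures will be used in order until one converges". Six structures follow: heterogeneous Toeplitz, heterogeneous autoregressive, heterogeneous compound symmetry, then the homogeneous form of each.
- **Discretion.** Just before naming the unstructured matrix, the SAP says that the model, "specifically the chosen covariance structure, is subject to change based on findings during model building".

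The same pairing of statements recurs in the code for the secondary endpoints (SAP 4.4.1.1.1 to 4.4.1.1.8) and for HbA1c (SAP 4.5.1). Protocol 9.3 names a mixed model for repeated measures but no covariance structure.

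**The concern.** An unstructured matrix already leaves every variance and covariance free. A random intercept adds the same constant to all of them, so the data cannot separate the two. A fitting routine may then report a singular Hessian or fail to converge. Under the SAP, failure to converge ends the use of the unstructured model, so the primary analysis could pass to a more restrictive structure because of a surplus term and not because the data were too thin.

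The second issue is pre-specification. The ordered list is a sound rule, but the sentence before it allows the structure to change on grounds that are not tied to convergence. Model building needs outcome data, and an open-label single-arm study has no blinded allocation to shield that choice. By contrast, SAP 4.3.1.1 rules out changes to the missed-dose algorithm once the database is locked. No such limit is stated for the model.

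**Working it through.** **Inputs.** Weekly values per participant: q = 6 (SAP 4.3.2 text and Table 4.1), or q = 5 under the competing statement after the code. Random intercept and unstructured residual matrix: SAP 4.3.2, text and code. The plan gives no parameter count to reproduce.

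**Step 1: count.** The covariance of one participant's values is V = R + tJ, where R is the residual matrix, t the intercept variance and J a matrix of ones.

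- q = 6: R has 6 × 7 / 2 = 21 free elements; adding t gives 22 parameters for the 21 distinct elements of V.
- q = 5: 5 × 6 / 2 = 15; adding t gives 16 for 15.

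Replacing R by R − cJ and t by t + c leaves V unchanged for any c that keeps R positive definite.

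**Step 2: rank check for every listed structure (q = 6).** The rank is that of the Jacobian of the distinct elements of V with respect to all covariance parameters, random intercept included.

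| Structure | Parameters | Rank |
|---|---|---|
| Unstructured | 22 | 21 |
| Heterogeneous Toeplitz | 12 | 12 |
| Heterogeneous autoregressive | 8 | 8 |
| Heterogeneous compound symmetry | 8 | 8 |
| Toeplitz | 7 | 6 |
| Autoregressive | 3 | 3 |
| Compound symmetry | 3 | 2 |

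The starting structure and the fourth and sixth fallbacks each carry one redundant parameter. With q = 5 the same three are deficient (16/15, 6/5 and 3/2).

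**Step 3: effect on the estimate.** In one simulated data set (32 participants, six weeks), the same V was split with intercept variance 0, 0.283, 0.566 and 1.076. All four splits gave log-likelihood −148.088645 and period effect 0.02807. The split is arbitrary; V and the period effect are not.

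**Step 4: effect on Kenward-Roger inference.** An illustrative calculation with 28 participants left week out of the fixed effects so that the period contrast was estimable. With a generalized inverse of the information matrix, the 22-parameter and 21-parameter forms gave the same standard error (0.41082) and the same degrees of freedom (27.0).

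**Step 5: does the choice of structure matter?** Null data were simulated with 32 participants, complete data and 300 runs. The assumed covariance was 4 × (0.35 + 0.65 × 0.5^|i−j|), a random intercept plus first-order autoregression. Each structure was fitted by REML without a random intercept, and the Weeks 15–18 minus Weeks 5–6 contrast was tested on n − 1 degrees of freedom. Rejection rates at a nominal 5%:

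- unstructured 4.7%, heterogeneous Toeplitz 5.0%, Toeplitz 4.7%
- heterogeneous autoregressive 2.0%, autoregressive 2.3%
- heterogeneous compound symmetry 12.7%, compound symmetry 13.3%
- smallest p-value of the seven: 13.7%

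The Monte Carlo standard error is about 1 to 2 percentage points. The documents do not give the true correlation pattern, so these rates are illustrative.

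**Step 6: sample size.** The 24 evaluable participants in Protocol Table 9.1 reproduce from a paired t-test. The SD of the difference is 0.419 × √(2 × (1 − 0.2)) = 0.530, and with a difference of 0.323 and n = 24 the power is 81.6%. The figure does not rest on the mixed model.

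**The case against.** The strongest reply has four parts.

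1. **The redundancy is harmless to inference.** Steps 3 and 4 show the same likelihood, the same period effect and, with a generalized inverse, the same Kenward-Roger result. This stands. A reader might infer that the primary estimate is biased, that the model cannot be fitted, or that its standard errors are wrong. The documents support none of these. They do not say whether the software would stop, warn or set a parameter to a boundary, so non-convergence is possible and not established. What remains is that the SAP ties a change of model to convergence and does not say how a singular-Hessian warning is to be treated.
2. **The fallback order is already fixed.** This also stands. The SAP names a starting structure and an order to be used only on non-convergence. A reader might infer a free choice of whichever structure gives the best p-value, but no section plans that, and the 13.7% in step 5 describes a practice that the SAP does not propose. The first fallback showed no inflation (5.0%).
3. **The findings referred to may simply be convergence findings.** That reading is possible, but the sentence does not say so, and the convergence rule follows separately.
4. **Departures would be disclosed.** Protocol 9.3 and SAP 4.1 require lesser changes of method to be described and justified in the study report. That makes a change visible afterwards; it does not make it pre-specified.

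**Conclusion.** Both parts hold, at modest size. As written, the primary model has one covariance parameter too many (22 against 21, or 16 against 15 on the five-measurement wording), and two of the six fallbacks share the fault. The consequence is procedural: a possible move off the unstructured model caused by the specification, repeated wherever the code is reused. The discretionary sentence is a separate weakness. It sits beside a good rule and undercuts it.

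The redundancy result is algebraic and needs no assumption about the data or the number of participants. The claim that the choice of structure can matter rests on the assumed correlation pattern in step 5 and should not be read as a forecast for this trial. The point is worth correcting before database lock, but it is not a reason to doubt the period estimate.

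**What to change.** - Remove the RANDOM statement from the unstructured, homogeneous Toeplitz and compound-symmetry models, in the primary code and in every section that repeats it. Qualify the text of SAP 4.3.2 that makes participant a random effect.
- State before database lock whether the random intercept is kept in the four identifiable fallbacks. There the intercept variance is a genuine parameter. In the two autoregressive structures in particular, dropping it gives a different model.
- Delete the sentence that leaves the covariance structure open to change.
- Keep the existing order, moving on only if the model without the redundant term fails to converge.
- Reconcile the two statements of how many Study Period 1 values enter the model.

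Without the random term, the unstructured model has 21 parameters for 21 elements and still captures all within-participant correlation. The cost is minor code and text edits; the 24 evaluable participants are unaffected.

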## 9.4. Sample Size Determination

This clinical study aims to enroll approximately 50 participants (i.e., with signed informed consent and meeting all eligibility criteria) in sites across France. This sample size provides ≥80% power to detect a mean difference of daily MBD of 0.323 between the unmasked and masked RMA periods.

The sample size also assumes:

- a conservative correlation estimate of 0.2 between the unmasked and masked RMA periods
- an SD of 0.419 for the mean difference, and
- a 2-sided alpha of <0.05 (Adolfsson et al. 2020).

The estimated mean difference of 0.323 daily MBD is equivalent to a clinically relevant improvement of approximately 2.3 fewer MBD per week in the unmasked RMA period compared to the masked RMA period (also approximately 11% improvement).

As this is a relatively new field with very limited data, a range of correlations and standard deviations was considered in the sample size calculation as well as varying dropout rates. Table 9.1 provides an overview of how the appropriate sample size was identified.

Table 9.1. Sample Sizes of Evaluable Participants Needed to Detect at Least a Mean Difference of 0.323 Missed Bolus Doses Per Day (Alpha=0.05, Power=80%)

Correlation	Standard deviation (SD)			
	0.4	0.419	0.5	0.6
0.2	22	24*	33	46
0.3	19	21	29	40
0.4	17	18	25	35
0.5	15	16	21	30

\*Note: represents appropriate sample size identified for current study.

A sample size of approximately 50 participants will be sufficient to allow:

- at least 24 participants will complete the study with analysable data (see Table 9.1 and Section 9.2.1)
- scope for increased variability (up to SD of 0.5)
- for non-analysable participants due to technical problems
- 35% dropout rate was assumed based on previous study results (Adolfsson et al. 2020, Gomez-Peralta et al. 2022,) and the impact of missing CGM data which would reduce the number of evaluable patients.

Participants who are entered but who do not proceed to the unmasked stage will be discontinued from the final efficacy analysis and may be replaced to ensure that enough participants complete the study. Best effort will be made to recruit an approximate ratio of 4:1 for T1D and T2D (approximately 40 participants with T1D and 10 participants with T2D) in this clinical study. Withdrawals will be monitored to ensure there are enough participants with T2D enrolled.

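### None of the six fallback covariance structures can let correlation drop across the nine-week gap between Weeks 6 and 15; if it does drop, the primary standard error is too small

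*SAP*

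**What the plan says.** SAP 4.3.2 fits a mixed model for repeated measures to six weekly values per participant, two from Study Period 1 and four from Study Period 2. The example code puts week in the CLASS statement, uses it as the repeated effect with an unstructured matrix, and adds a random participant effect. For non-convergence the rule is: "If this structure fails to converge, the following covariance structures will be used in order until one converges". The list opens with "Toeplitz with heterogeneity", then heterogeneous autoregressive, heterogeneous compound symmetry, and the homogeneous versions of the same three. No structure based on elapsed time, no period-block structure and no robust variance is listed. The same section also allows the covariance structure to change during model building.

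Protocol 9.4 plans on "a conservative correlation estimate of 0.2 between the unmasked and masked RMA periods", and Table 9.1 varies this from 0.2 to 0.5. Neither document gives a correlation between weeks within a period.

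**The concern.** The primary contrast compares one block of weeks with another, and the blocks are nine weeks apart. Its standard error depends on how strongly weeks correlate within a block and across the gap. Because week is a class variable, Toeplitz and autoregressive structures know only its rank order: Weeks 6 and 15 are forced to share the correlation of Weeks 15 and 16. Compound symmetry forces all fifteen pairs to one value. If correlation really is lower across the gap, each structure compromises by overstating the between-block correlation, understating the within-block correlation, or both. Either error shrinks the standard error, and Kenward-Roger degrees of freedom do not correct a misspecified covariance. The two-sided 5% level of the primary test is at stake.

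Reaching the fallback is a realistic prospect. An unstructured 6×6 matrix has 6×7/2 = 21 parameters, and the code adds a random-intercept variance that the matrix already absorbs, with about 24 to 32 evaluable participants.

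**Working it through.** **Inputs.** From Protocol 9.4: effect 0.323 per day, SD 0.419, correlation 0.2, "a 2-sided alpha of <0.05", 80% power, and "at least 24 participants will complete the study with analysable data". With 35% dropout, 50 × 0.65 = 32.5, so about 32. From SAP 4.3.2: the six weeks and the fallback list. Assumed: the within-period weekly correlation.

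**Plan's own figure.** A paired t-test with SD of the difference = SD × √(2(1 − r)) = 0.419 × √1.6 = 0.530 and a noncentral t gives n = 24. The same formula reproduces all 16 cells of Table 9.1. Reading 0.419 as the SD of the difference itself gives 16, so the planning analysis is a paired comparison of two period averages with 0.419 as the per-period SD.

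**Method.** Let w be the correlation between weeks in the same period, b the correlation between weeks in different periods, and r the correlation of the two period averages, with unit variances. Then b = r × √[((1+w)/2) × ((1+3w)/4)].

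The contrast is mean(Weeks 15–18) minus mean(Weeks 5–6), with week means fitted. Its true variance per participant is (1+w)/2 + (1+3w)/4 − 2b. For each fallback, take the best-fitting (likelihood) version of that structure and compute its variance for the same contrast. With SE ratio q = model SE / true SE, the large-sample rejection rate is 2Φ(−1.96q).

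**Compound symmetry by hand, r = 0.2, w = 0.6.**
- b = 0.2 × √(0.8 × 0.7) = 0.150. True variance = 0.8 + 0.7 − 0.299 = 1.201.
- Seven pairs lie within a period and eight across. The fitted common correlation is their average: (7 × 0.6 + 8 × 0.150)/15 = 0.360.
- Model variance = (1/2 + 1/4) × (1 − 0.360) = 0.480.
- q = √(0.480/1.201) = 0.632, so rejection = 2Φ(−1.24) = 21.5%.

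**All families, large-sample rejection rate.** The autoregressive structure keeps the SAP's random intercept.

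| r (between) | w (within) | Toeplitz, heterogeneous | Toeplitz | Autoregressive | Compound symmetry (het. – hom.) |
|---|---|---|---|---|---|
| 0.2 | 0.3 | 8.0% | 8.1% | 8.7% | 10.7–11.0% |
| 0.2 | 0.5 | 10.5% | 11.0% | 12.0% | 17.0–17.8% |
| 0.2 | 0.6 | 11.6% | 12.4% | 13.4% | 20.3–21.5% |
| 0.2 | 0.7 | 12.7% | 13.9% | 14.7% | 23.6–25.4% |
| 0.5 | 0.3 | 5.4% | 5.5% | 5.5% | 5.7–5.8% |
| 0.5 | 0.6 | 9.6% | 10.0% | 11.1% | 15.1–15.8% |
| all pairs equal | – | 5.0% | 5.0% | 5.0% | 5.0% |

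**Small-sample check.** In 400 simulated trials per setting (Monte Carlo error about 1 point), at r = 0.2 and w = 0.6:
- n = 24: heterogeneous Toeplitz 10.2%, compound symmetry 17.8–19.2%.
- n = 32: heterogeneous Toeplitz 11.8%, compound symmetry 18.5–20.5%.

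The unstructured matrix, equivalent here to a paired test of period averages, gave 3.8–5.8% in every setting.

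**Candidate replacements.** A random intercept plus a random participant-by-StudyPeriod effect gave 5.0–5.1% in every scenario, including a random intercept with weekly autoregressive decay. Spatial power on actual week number plus a random intercept gave 5.0% under that decay, but 7.2–8.1% when within-period correlation is flat at 0.3 to 0.7 and r = 0.2.

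**Limits.** Complete data, equal variances, no BMI or HbA1c covariates, and Satterthwaite-type degrees of freedom in place of Kenward-Roger. With both StudyPeriod and class week in the model, the StudyPeriod least-squares-mean difference is not estimable as coded, so the figures refer to the explicit contrast above.

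**The case against.** The strongest reply is that the inflation is conditional. The sample size section says nothing about neighbouring weeks, so a reader who infers that it assumes high within-period correlation goes beyond the text. If all six weeks are equally correlated, the model variance and the true variance are both 0.75(1 − correlation), and every fallback has the right size. That stands, but it is a narrow escape at the planning value. Equal correlation of about 0.08 is needed to give a period-average correlation of 0.2, since 0.08/√(0.54 × 0.31) ≈ 0.2. At 0.5 the equal correlation is about 0.27. Any higher correlation between weeks of the same period means that correlation falls across the gap.

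The order of the list also matters. Rates near 20% belong to compound symmetry, which is third (heterogeneous) or last (homogeneous); they are not the expected result of the first fallback.

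Nor is it shown that the fallback will probably be used. With complete data on 24 participants a 6×6 unstructured matrix is estimable, and the weak spot is the redundant random effect. The clause allowing changes during model building means the list is not strictly binding, though that is a reason to have a sound list rather than a defence of this one.

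Table 4.1 shows week as text, and a reader might infer that alphabetical sorting makes matters worse. Putting Weeks 15–18 before Weeks 5–6 left Toeplitz rejection unchanged in every scenario with flat within-period correlation.

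**Conclusion.** The point holds conditionally. It can be read from the SAP that no listed fallback can represent a fall in correlation across the gap. How far this inflates the primary test depends on a within-period correlation that the documents do not give. At the planning between-period correlation of 0.2 and an assumed within-period correlation of 0.3 to 0.7, rejection is about 8–14% under Toeplitz (8–13% for the heterogeneous form listed first), 9–15% under autoregressive with the random intercept, and 11–25% under compound symmetry. At between-period 0.5 and within-period 0.3 it is 5.4–5.8%, and with equal correlation throughout it is 5%.

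The documents do not support the stronger statements that the standard error is always too small, or that a 20% error rate is to be expected. The concern applies only if the unstructured model fails and the listed rule is followed.

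**What to change.** 1. Drop the RANDOM statement from the unstructured model. It is redundant there and invites non-convergence.
2. Replace the six-item list with one model: a random intercept plus a random participant-by-StudyPeriod effect. Write the primary comparison as the explicit contrast of the two period averages.
3. As last resort, specify a paired analysis of each participant's Weeks 15–18 mean minus Weeks 5–6 mean. This is the calculation that reproduces Table 9.1. State how early discontinuers without Weeks 15–18 data are handled, because the main analysis set admits participants who stop early with at least 20 days of CGM data anywhere in Weeks 7–18.
4. Do not put spatial power plus a random intercept first, given its 7–8% rejection when within-period correlation is flat.
5. Carry the same change into the secondary models that reuse this code.

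The cost is SAP wording, a few lines of code and possibly a wider confidence interval for the primary difference.

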4.3.3. Sensitivity Analysis

4.3.3.1. Varying Definitions of Missed Bolus Dose

Sensitivity analysis will be performed for the primary endpoint on the sensitivity analysis set. Varying definitions of MBD will be conducted as sensitivity analyses using a mixed-effect models for repeated measures as described in Section 4.3.2. The analyses will be completed in the sensitivity analysis set.

These include:

- MBD interval definition: 2 hours prior and 2 hours after start of glucose excursion (-2, 2), and
- MBD glucose excursion: ≥80 mg/dL (>4.4 mmol/L) rise within 2 hours.

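### SAP 4.3.2 describes a primary model without a week effect but prints code with one, and the printed code cannot return the period difference

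*SAP*

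**What the plan says.** SAP 4.3.2 sets out the primary model in words before the code: "The study period will be a fixed effect, baseline body mass index (BMI) and baseline HbA1c as covariates, and subject as the random effect". Week appears there only as the repeated measure. After the code, the SAP explains its own program in the same way: "the model statement contains the outcome, the fixed effect (study period), and the covariates (baseline BMI and baseline HbA1c"), with time left to the REPEATED statement.

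The program printed between these two descriptions differs. Week is listed in CLASS and also enters the fixed effects: "Model Weekly_Average_MBD = StudyPeriod BaseBMI BaseHbA1c week". The primary result is then requested with "Lsmeans StudyPeriod/diff cl pdiff". The SAP says that the difference between the two period means, its two-sided 95% confidence interval and its p-value will be reported.

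The number of rows in Study Period 1 is also inconsistent. Before the code the repeated measure is "2 weeks in Study Period 1 and 4 weeks in Study Period 2 for each participant". After it, "there will be 1 measurement in Study Period 1 and 4 measurements in Study Period 2 for each participant". Table 4.1 shows two Study Period 1 rows.

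On covariance: "An unstructured covariance structure will be used to model the within-participant errors". Both the text and the code add a random subject effect to this.

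**The concern.** Every analysed week belongs to exactly one period. Once week is a categorical fixed effect, study period carries no further information, and the difference between the period means cannot be separated from the week effects. The printed code would therefore fail to deliver the trial's primary estimate, interval and p-value.

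Someone must then choose a repair, and the SAP does not say which model is the planned one. Dropping week, and keeping week with an averaged contrast, weight the weeks differently and can give different answers if missed boluses drift within a period. In an open-label, single-arm study that choice should not be left until results are visible.

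The same MODEL terms recur in the nine secondary code blocks of SAP 4.4.1.1. The varying-definition analyses are run "using a mixed-effect models for repeated measures as described in Section 4.3.2", and the supplementary analysis in SAP 4.3.4 inherits the primary model apart from BMI.

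**Working it through.** **1. Inputs.** From SAP 4.3.2: analysed weeks 5, 6 (Period 1) and 15, 16, 17, 18 (Period 2), and the model terms in the text and in the code. The illustrative mean profile is Table 4.1: 10.3, 9.6, 10.1, 8.2, 7.6, 5.2. The rank check uses 32 participants (50 x 0.65 = 32.5, from the 35% dropout assumption), but the result does not depend on this number.

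**2. The plan's own figures.** Table 4.1 gives a baseline of (10.3 + 9.6)/2 = 9.95, which is correct. The Weeks 15 to 18 mean is (10.1 + 8.2 + 7.6 + 5.2)/4 = 7.775, so the equal-weight period difference is 7.775 - 9.95 = -2.175 per week. The required 24 evaluable participants also reproduces, from a paired t-test with difference SD 0.419 x sqrt(2 x (1 - 0.2)) = 0.530 (power 81.6%). That calculation does not use the mixed model and is unaffected.

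**3. Estimability.** A linear function is estimable only if appending its coefficient row to the design matrix leaves the rank unchanged.

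| Model | Columns | Rank | Rank without StudyPeriod | Rank with period difference appended | Period difference |
|---|---|---|---|---|---|
| Printed code, 6 rows per participant | 11 | 8 | 8 | 9 | non-estimable |
| Printed code, 1 Period 1 row (5 rows) | 10 | 7 | 7 | 8 | non-estimable |
| Model in the text | 5 | 4 | not needed | 4 | estimable |

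The 11 columns are the intercept, 2 periods, BMI, HbA1c and 6 weeks. Study period has 0 degrees of freedom after week. Both period means also fail the check, because the default coefficients put 1/6 on every week. With coefficients nested in period (1/2 on Weeks 5 and 6, 1/4 on Weeks 15 to 18) the rank stays at 8, so that contrast is estimable. These results are algebraic; PROC MIXED was not run.

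**4. Do the repairs agree?** Week nested in period gives the equal-weight contrast, -2.175, whatever the covariance. The model without week gives the generalised least squares estimate, with weights (X'V⁻¹X)⁻¹X'V⁻¹. Using the Table 4.1 profile as the mean, with assumed V:

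| Assumed covariance | Model without week | Equal-weight contrast |
|---|---|---|
| Compound symmetry, correlation 0.5 | -2.18 | -2.175 |
| Autoregressive, 0.8 per calendar week | -1.93 | -2.175 |
| Autoregressive, 0.6 per visit | -0.78 | -2.175 |
| Correlation 0.5, SD falling from 3.0 to 1.5 over Weeks 15 to 18 | -2.38 | -2.175 |

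In the per-visit case Week 15 gets weight 0.70 and Weeks 16 and 17 get 0.07 each. For scale, the planned effect is 0.323 x 7 = 2.26 per week. Without drift within a period, both models target the same value.

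**5. Smaller points.**
- A random intercept plus an unstructured 6 x 6 matrix has 22 parameters for 21 distinct elements. Homogeneous Toeplitz (7 for 6) and homogeneous compound symmetry (3 for 2) on the fallback list are also over-parameterised. The marginal covariance is unchanged.
- SAP 4.5.1 models one HbA1c change per participant, so neither study period nor week varies (5 columns, rank 3). This is a separate, exploratory defect, not the same aliasing.

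**The case against.** The text already names an estimable model, twice. The program is labelled as an example, and even its degrees-of-freedom option is misspelt. The failure would also be visible: the code returns no estimate rather than a wrong one, and deleting one word restores the described model. This is fair, and it means that no data or conclusion is lost. But no rule in the SAP gives the text precedence, the explanation after the code misdescribes that very code, and the same term appears in every secondary block. The clause allowing model details to change names specifically the covariance structure and does not settle whether week is a fixed effect.

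The illustration of differing repairs can also be called extreme. It uses one hypothetical participant's profile as the population mean, and the -0.78 case treats the gap from Week 6 to Week 15 as one step. With 0.6 per calendar week the model without week gives -2.21. With one fifth of the drift, the last three cases become -2.13, -1.90 and -2.22. So the size of the difference is uncertain and may be small. The per-visit case is still relevant, because a standard autoregressive fallback spaces visits equally.

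Equal weighting is not fully settled by the documents either: SAP 4.3.1.1 also defines a period rate per evaluable CGM day. This supports stating the choice explicitly.

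**Conclusion.** The concern holds. SAP 4.3.2 contains two different primary models, and the one in code cannot produce the stated primary result. This follows from the design alone and does not depend on sample size, missing data, covariance structure or the number of Study Period 1 rows. Ten code blocks share the aliasing (one primary, nine secondary); the HbA1c block has its own defect.

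The model in the text is estimable, so the primary analysis can be recovered. The gap between repairs, 0 to about 1.4 missed boluses per week in the four cases shown (2.175 - 0.78 = 1.395), rests on assumed covariances and on the drift in Table 4.1. It vanishes if there is no drift. Correction is needed before database lock; that deadline is this review's, since the SAP mentions the lock only for the missed-bolus algorithm.

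**What to change.** 1. Make text and code agree on one estimable model. Preferred: `MODEL Weekly_Average_MBD = StudyPeriod week(StudyPeriod) BaseBMI BaseHbA1c` with `LSMEANS StudyPeriod / diff cl`, which weights weeks equally within each period. Equivalent: week only, with a pre-specified contrast of the Weeks 15 to 18 mean minus the Weeks 5 and 6 mean. In that version week must be numeric or have a fixed level order: the text labels of Table 4.1 sort Weeks 15 to 18 first, and calendar-order coefficients would then give -0.975 instead of -2.175. Minimal alternative: delete week from MODEL and state that weeks are weighted by the estimated covariance.
2. Apply the choice to all secondary, sensitivity and supplementary models, and settle whether Study Period 1 contributes two weekly rows or one.
3. Minor: remove the RANDOM statement under the unstructured matrix and under homogeneous Toeplitz and compound symmetry, and state that the fallback order is binding.
4. Minor: replace the HbA1c mixed model with a one-sample or paired analysis of the Visit 1 to Visit 7 change.

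The cost is a SAP text and code correction, with no new data and no additional participants.
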